10.7. Safety Analyses

The analysis of safety will be based on the Safety Population, comparing patients in the two randomized arms: apixaban vs. dalteparin. AEs will be mapped to system organ classes and preferred terms in MedDRA. Treatment emergent events, defined as those that start or worsen after the start of apixaban/dalteparin AEs, will be summarized by treatment group, system organ class, and preferred term, and also by event severity and by the event's relationship to study treatment. At each level of summation, patients will be counted only once, under the greatest severity and strongest study-drug relationship (as reported by the investigator). Clinical laboratory data will be summarized for each treatment group at each measurement time point and for each patient's final post-baseline measurement in the following ways: (1) with descriptive statistics (mean, standard deviation, median, and range) for each measurement time point; (2) with descriptive statistics for the change from baseline in the measurements at each post-baseline time point; and (3) with shift tables summarizing the frequencies of patients below, within, and above the normal ranges at each time point as compared with baseline. All clinical laboratory values collected during the study will be listed, with values outside the normal ranges flagged for clinical evaluation. Concomitant medications will be summarized by treatment group based on mapping to drug classes and generic terms in the WHO Drug Dictionary.

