9.2 Collection, Reporting and Documentation of AEs

This study will follow a targeted approach to AE and SAE collection and reporting. All AEs occurring after the subject signs the ICF and through Month 6 or the global EOT date, whichever occurs first, whether observed by the Investigator or reported by the subject, will be recorded on the Adverse Events section of the eCRF if they fulfill one of the following criteria:

- 1) meet seriousness criteria;
- 2) result in interruption or discontinuation of the assigned study drug;
- 3) meet criteria as a study outcome; or
- 4) an event of special interest.

All laboratory, vital sign, or electrocardiogram (ECG) values should be evaluated by the Investigator regarding clinical significance. Isolated abnormal laboratory results or vital sign findings or ECG findings should be reported as AEs if they are symptomatic, result in study drug discontinuation, require corrective treatment, or are otherwise defined as an AE of Special Interest (AESI).

Clinically significant abnormal laboratory findings associated with the subject's cancer or other pre-existing conditions will not be reported as AEs or SAEs unless judged by the Investigator as more severe than expected for the subject's condition and meet the criteria for targeted AE and SAE reporting.

Medical conditions (including laboratory values/vital signs that are out of range) that were diagnosed or known to exist prior to informed consent will be recorded as part of medical history.

All SAEs occurring after informed consent for study participation has been obtained, which are considered not related with the subject's cancer or other pre-existing conditions,

are to be reported according to the procedures for Serious Adverse Event Reporting-Procedure for Investigators.

A preplanned (prior to signing the Informed Consent Form) procedure or treatment requiring hospitalization for pre-existing conditions which do not worsen in severity should not be reported as SAEs.

For deaths, the underlying or immediate cause of death should always be reported as an SAE. When a subject dies from disease progression of pre-existing cancer with no other immediate causes, "disease progression" should be reported as an SAE. In addition, any serious, untoward event that may occur subsequent to the reporting period that the Investigator assesses as related to study drug should also be reported and managed as an SAE.

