### 10.9.1 Adverse events

All adverse events recorded during the treatment period and up to 30 days after the last study dose intake will be summarized by treatment group with descriptive statistics for the Safety population.

All adverse events will be assigned to a Preferred Term (PT) and will be classified by primary System Organ Class (SOC) according to the MedDRA thesaurus version 20.1. Adverse events will be reported on a per-patient basis. This means that even if a patient reports the same event repeatedly (i.e. events mapped to the preferred term) the event will be counted only once. In the latter case, the event will be assigned the worst intensity and the strongest relationship to the study drug.

For summaries, the drug-event relationship will be shown as “*Related*” if relationship with study treatment is assessed as “*Certain*”, “*Probable*” or “*Possible*” by the Investigator; otherwise the event is considered as “*Unrelated*”. Missing categories will be considered as related.

Treatment emergent events, defined as those AEs that start or worsen after the start of apixaban/dalteparin and up to 30 days after the last study dose intake, will be summarized by treatment group, System Organ Class, and Preferred Term, and also by event severity and by the event’s relationship to study treatment.

The following listing and tables will be presented:

- 1) An overview of adverse events with the number of patients who exhibited at least one AE, number of adverse events, number of patients who exhibited at least one TEAE, number of TEAEs, number of patients who reported at least one related TEAE, number of related TEAEs, number of patients who reported at least one treatment-emergent serious adverse event (TESAE), number of TESAEs, number of patients who reported at least one related TESAE, number of related TESAEs, number of patients who reported at least one AESI, number of AESI, number of patients who died, number of patients who temporarily discontinued the study drug due to an adverse event, number of patients with premature

withdrawal due to an adverse event;

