- 2) An overview of adverse events with the number of patients who exhibited at least one TEAE with DVT as study outcome, number of TEAEs with DVT as study outcome, number of patients who exhibited at least one TEAE with PE as study outcome, number of TEAEs with PE as study outcome, number of patients who reported at least one TEAE with bleeding as study outcome, number of TEAEs with bleeding as study outcome, number of patients who reported at least one TEAE with major bleeding as study outcome, number of TEAEs with major bleeding as study outcome, number of patients who reported at least one TEAE with clinically relevant non-major bleeding as study outcome, number of TEAEs with clinically relevant non-major bleeding as study outcome, number of patients who reported at least one TEAE with clinically relevant bleeding as study outcome, number of TEAEs with clinically relevant bleeding as study outcome, number of patients who reported at least one TEAE with myocardial infarction as study outcome, number of TEAEs with myocardial infarction as study outcome, number of patients who reported at least one TEAE with ischemic stroke as study outcome, number of TEAEs with ischemic stroke as study outcome, number of patients who reported at least one TEAE with other venous thrombotic events as study outcome, number of TEAEs with other venous thrombotic events as study outcome, number of patients who reported at least one TEAE with other arterial thrombotic events as study outcome, number of TEAEs with other arterial thrombotic events as study outcome.
- 3) Summary of all TEAEs by treatment group, primary System Organ Class and Preferred Term;
- 4) Summary of all TEAEs by treatment group, primary System Organ Class, Preferred Term and Intensity;
- 5) Summary of all TESAEs by treatment group, primary System Organ Class and Preferred Term;
- 6) Summary of all non-serious TEAEs by treatment group, primary System Organ Class and Preferred Term (where PT occurred at a frequency of  $\geq 5\%$ );
- 7) Summary of all Related TEAEs by treatment group, primary System Organ Class and Preferred Term;
- 8) Summary of all Related TESAEs by treatment group, primary System Organ Class and Preferred Term;
- 9) Summary of all AESI by treatment group, primary System Organ Class and Preferred Term;
- 10) Patient Listing of Deaths;
- 11) List of TEAEs by patient;
- 12) List of TESAEs by patient;
- 13) List of Related TEAEs by patient;
- 14) List of Related TESAEs by patient;

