- 15) List of AESI by patient;
- 16) List of Patients with Adverse Events Leading to Withdrawal from study drug;
- 17) List of Patients with Adverse Events Leading to temporary discontinuation of study drug.

The number and the percentage of patients with at least one TEAEs by SOC and Preferred Term, and the number of events will be presented for the statistical summary from the above points #3 to

#9.

Adverse events with start date before the first study dose intake or after 30 days the last study dose intake will be only listed.

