### ALGORITHM FOR TREATMENT EMERGENCE OF ADVERSE EVENTS:

START DATE	STOP DATE	ACTION
Known	Known	If start date < study med start date, then not TEAE If start date >= study med start date but ≤ study med end date+30, then TEAE
	Partial	If start date < study med start date, then not TEAE If start date >= study med start date but ≤ study med end date+30, then TEAE
	Missing	If start date < study med start date, then not TEAE If start date >= study med start date but ≤ study med end date+30, then TEAE
Partial, but known components show that it cannot be on or after study med start date	Known	Not TEAE
	Partial	Not TEAE
	Missing	Not TEAE
Partial, could be on or after study med start date	Known	If stop date < study med start date, then not TEAE If stop date >= study med start date but ≤ study med end date+30, then TEAE
	Partial	Impute stop date as latest possible date (i.e. last day of month if day unknown or 31st December if day and month are unknown), then: If stop date < study med start date, then not TEAE If stop date >= study med start date but ≤ study med end date+30, then TEAE
	Missing	Assumed TEAE
Missing	Known	If stop date < study med start date, then not TEAE If stop date >= study med start date but ≤ study med end date+30, then TEAE
	Partial	Impute stop date as latest possible date (i.e. last day of month if day unknown or 31st December if day and month are unknown), then: If stop date < study med start date, then not TEAE If stop date >= study med start date but ≤ study med end date+30, then TEAE
	Missing	Assumed TEAE

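### The SAP's date-only rules leave a pre-dose adverse event that worsens on study drug out of the TEAE tables if it keeps its original onset date, contrary to the plan's own definition

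*Protocol*

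**What the plan says.** Two passages give the definition. Protocol 10.7 has "Treatment emergent events, defined as those that start or worsen after the start of apixaban/dalteparin AEs" (the last word looks misplaced, but the sense is clear). SAP 10.9.1 has "defined as those AEs that start or worsen after the start of apixaban/dalteparin and up to 30 days after the last study dose intake". Both treat onset and worsening as alternative routes into the category.

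Two passages in the SAP give the working rules. In the treatment-emergence algorithm of SAP 12, an event with a known start date is handled by "If start date < study med start date, then not TEAE", whatever is known of its stop date. An event whose start date is "Partial, but known components show that it cannot be on or after study med start date" is likewise never a TEAE. SAP 10.9.1 adds: "Adverse events with start date before the first study dose intake or after 30 days the last study dose intake will be only listed".

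On collection, Protocol 9.2 records "All AEs occurring after the subject signs the ICF and through Month 6 or the global EOT date", whichever comes first, if they meet one of four targeted criteria. The schedules of assessments (Protocol Appendix 3 and SAP Table 1) instead start AE/SAE collection at the first study drug administration.

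**The concern.** A programmer cannot satisfy both the definition and the algorithm. No row of SAP 12 takes worsening, a change of intensity or a change to serious as an input. For an event known to precede the first dose, the worsening half of the definition therefore does nothing.

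The flag matters because most of the adverse-event output rests on it: the overview counts, the overview of TEAEs with study outcomes, the tables by intensity and by relationship, and outputs such as "Summary of all TESAEs by treatment group, primary System Organ Class and Preferred Term". A wrongly cleared flag removes the patient's event from all of these at once and leaves it only in a listing.

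Such events can arise. Under Protocol 9.2 the collection window opens at consent, screening may precede enrolment by up to 72 hours, and Protocol 4.2.2 tolerates up to 72 hours of therapeutic heparin before randomization. Targeted collection adds a route: a non-serious event that begins before dosing may become recordable only when it turns serious on drug. If the site then dates it at its true onset, the algorithm excludes the very record that the worsening created.

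**Working it through.** There is no planned figure to reproduce, so the check is a trace of the rules. Inputs: the definition in Protocol 10.7 and SAP 10.9.1, the algorithm in SAP 12, and the AE definition in Protocol 9.1. For illustration, take first dose as day 0 and last dose as day 180, so the window closes on day 180 + 30 = 210.

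- Definition: TEAE if start ≥ 0, or if worsening falls between day 0 and day 210.
- Algorithm, start known: TEAE if 0 ≤ start ≤ 210; not TEAE if start < 0.
- Algorithm, partial start certainly before dose: not TEAE.
- Algorithm, start missing, or partial and possibly on or after dose: decided by the stop date; assumed TEAE if the stop date is missing.

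| Case | Definition | SAP 12 |
|---|---|---|
| 1. Known start day −1, worsens day 10, stops day 20 | TEAE | not TEAE |
| 2. As case 1, stop date missing | TEAE | not TEAE |
| 3. Partial start certainly before dose, worsens day 10, stops day 20 | TEAE | not TEAE |
| 4. Partial start possibly on or after dose (truly day −1), worsens day 10, stops day 20 | TEAE | TEAE |
| 5. Start and stop missing, truly began day −1, never worsens | not TEAE | TEAE (assumed) |
| 6. Worsening entered as a new record starting day 10 | TEAE | TEAE |

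Cases 1 to 3 are the defect. Case 4 agrees only because the ambiguous date lets the stop date decide, not because worsening was tested. Case 5 errs in the other direction. Case 6 shows that the algorithm gives the intended answer when the worsening has its own record and date.

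The outcome therefore turns on data entry. Protocol 9.1 includes worsening of a pre-existing condition on study drug in its AE definition, so case 6 is permitted. However, Protocol 9.2 asks for onset, duration, intensity and seriousness for each AE, and asks for neither a date of worsening nor serial intensities. Neither document says whether a worsening opens a new record or updates the old one. The SAP 10.9.1 rule that a repeated event takes its worst intensity does not settle which date applies.

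**The case against.** The strongest reply is that very few events can be affected.

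- Protocol 9.2 collects only AEs that are serious, interrupt or stop study drug, are study outcomes, or are of special interest. It sends conditions known before consent to medical history.
- If sites follow the schedules of assessments, collection starts at first dose and most records of this kind never exist.
- A worsening entered as its own AE is counted correctly.

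All of this stands and bears on frequency. It does not make the definition and the rules agree, and the conflict between Protocol 9.2 and the schedules is itself something to settle.

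A reader might infer that every pre-dose event is excluded, or that the error always undercounts. The documents do not support either: the rows for missing or ambiguous start dates can admit pre-dose events, even ones that never worsened (cases 4 and 5). Undercounting is the right description only for events known to have begun before first dose.

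A reader might also infer that major bleeding is understated. Active bleeding is an exclusion (Protocol 4.2.2), and eligibility is rechecked at enrolment (Protocol 6.4). The primary safety endpoint (SAP 9.12.3), the adjudicated on-treatment bleeding analyses (SAP 5.2 and 10.9) and the outcome tabulations (SAP 10.9.1.1) are not stated to depend on the TEAE flag. Progression of a laboratory abnormality would still show in the change-from-baseline and shift tables of SAP 10.9.2.

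Finally, a rule that relies only on detecting an increase in intensity might not be programmable from the fields that Protocol 9.2 lists. That objection is sound and shapes the fix.

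**Conclusion.** The point holds as an error in the working rules. The conflict lies mainly within the SAP, whose section 12 and listing-only sentence contradict its own definition as well as the protocol's. It misclassifies an event when three conditions meet: the event is known to have begun before first dose, it worsens between first dose and last dose + 30 days, and its record keeps the original onset date.

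The documents give no rate for such events. The number is probably small, and any figure would be guesswork. The consequence is confined to the descriptive TEAE and TESAE summaries, including the overview of TEAEs with study outcomes. No effect is shown on the primary efficacy analysis or on the adjudicated on-treatment bleeding analyses, and nothing in the documents suggests a difference between arms.

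It is still worth correcting. The tables would not match their stated definition, and in an open-label trial the choice between two conflicting rules should not be left to programming. Protocol 10.9 requires approval of the SAP before un-blinding, which is the point by which to settle it.

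**What to change.** 1. In the eCRF guidance, require any worsening on or after first dose (an increase in intensity or a change to serious) to be entered as a separate AE record whose start date is the date of worsening.
2. In SAP 12, state that such records are classified by that date. Add that a record with a pre-dose onset is a TEAE if the data show that it worsened between first dose and last dose + 30 days. Apply this second rule only where no separate record exists, so that one worsening is not counted as two events.
3. Amend the listing-only sentence in SAP 10.9.1 so that it excepts events that worsened in that window.
4. Reconcile the start of AE collection between Protocol 9.2 (consent) and the schedules in Protocol Appendix 3 and SAP Table 1 (first dose).

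The cost is a line of site guidance, a few sentences of SAP text, one more derivation and slightly higher TEAE counts. No endpoint, sample size or clinical procedure changes.

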10.8. Subgroup Analyses

Pre-specified subgroup analyses will be planned and reported in the statistical analysis plan before the un-blinding of the study.

Interim Analyses

No interim analysis is planned.

10.9. Detailed Statistical Analysis Plan

A detailed statistical analysis plan will be drafted, reviewed and approved by the Steering Committee prior of the un-blinding of the data.

11. FEASIBILITY

Overall, about 140 study centers in Europe and USA, will participate in the study. Each study center is expected to recruit not less than 10 patients in the 18-month recruitment period. The overall study duration (first patient in/last patient out) is estimated to be 25 months.

12. INSURANCE

All subjects participating in the study will have insurance coverage by the Promoter, which is in line with applicable laws and/or regulations.

13. PROMOTER

The Promoter of the study is FADOI Foundation.

15. APPENDICES

Appendix 1 – Concomitant medications

1. Prohibited Concomitant Medications

Specifically excluded concomitant medications and cautions regarding other concomitant medications are provided below. The list in this appendix reflects exclusionary concomitant medications at the beginning of the study. If there are changes to this list during the study, the changes will be provided as an update to this appendix, but will not be considered a protocol amendment.

1.1. Antiplatelet Drugs

Dual antiplatelet therapy (any 2 antiplatelet agents including aspirin plus any other oral or IV antiplatelet drug) is prohibited while on study drug. If a clinical indication for dual antiplatelet therapy arises after randomization (eg, placement of an intracoronary stent), study drug should be interrupted and use of open-label LMWH/VKA is permitted at the physician's discretion.

Use of any antiplatelet medication, including aspirin, as single agent antiplatelet therapy is allowed while on study drug.

It is strongly encouraged to restrict the dose of aspirin (if indicated) to \leq 100 mg daily, although higher doses are permitted for a strong clinical indication (eg, development of an acute MI).

Examples of non-aspirin oral antiplatelet agents include the following:

- Thienopyridines: clopidogrel (Plavix®), ticlopidine (Ticlid®), prasugrel
- (EffientTM)
- Dipyridamole: Persantine®, Aggrenox®
- Pentoxifylline (Trental®)

- Sulfinpyrazone (Anturane®)
- Ticagrelor (Brilinta®)
- Cilostazol (Pletal®)

IV antiplatelet agents include the following:

- Glycoprotein IIb/IIIa inhibitors: Abciximab (ReoProTM), Eptifibatide
- (Integrilin®), Tirofiban (Aggrastat®)
- PGY12 Inhibitor: Cangrelor
- Dextran

1.2. Oral Anticoagulants Other Than Study Drug

Oral anticoagulants including vitamin K antagonists (eg, warfarin), Factor IIa inhibitors (eg, dabigatran), and FXa inhibitors (eg, rivaroxaban, edoxaban) after randomization are prohibited (unless used to bridge a temporary study drug interruption). The only allowed oral antithrombotics are the study drugs.

1.3. Parenteral Anticoagulants

Parenteral anticoagulants such as heparin, LMWHs, direct thrombin inhibitors, and FXa inhibitors are prohibited except as specifically outlined in the protocol. For instance, LMWHs are allowed as lead-in therapy prior to edoxaban administration. Examples of prohibited parenteral anticoagulant medications, when used contrary to protocol specifications, include the following:

- Low molecular weight heparins: dalteparin (Fragmin®), tinzaparin (Innohep®,
- Logiparin®), reviparin (Clivarin®), nadroparin (Fraxiparine®), ardeparin (Normiflo®), certoparin (Sandoparin®), parnaparin (Fluxum®)
- Direct thrombin inhibitors: bivalirudin (Angiomax®), argatroban (Acova®), desirudin (Ipravask®), lepirudin (Refludan®)

- FXa inhibitors: fondaparinux (Arixtra®)

1.4. Intravenous Fibrinolytics

Examples of fibrinolytics include the following:

- Tissue plasminogen activator (alteplase, Activase®)
- TNK (tenecteplase, TNKase®)
- rPA (reteplase, Retavase®)
- Streptokinase (Streptase®)
- Anistreplase (Eminase®)

If a subject requires treatment with a fibrinolytic agent, then study drug must be interrupted while the subject is taking the fibrinolytic drug and at least 24 hours after administration of a fibrinolytic agent.

1.5. NSAIDs (Excluding Aspirin)

While on study drug, NSAIDs cannot be taken for ≥ 4 days per week. Less frequent use of NSAIDs is permitted while on study drug. However, the Investigator should weigh the benefit/risk of NSAID use in combination with an oral anticoagulant for the individual subject. Examples of NSAIDs include the following:

1.6. COX-2 Inhibitors

While on study drug, COX-2 inhibitors cannot be taken for ≥ 4 days per week. Less frequent use of COX-2 inhibitors is permitted while on study drug. However, the Investigator should weigh the benefit/risk of COX-2 inhibitor use in combination with an oral anticoagulant for the individual subject.

1.7. Strong inhibitors of both CYP3A4 and P-gp:

- atazanavir
- boceprevir
- clarithromycin
- conivaptan
- darunavir
- darunavir/ritonavir
- erythromycin
- indinavir
- indinavir/ritonavir
- itraconazole
- ketoconazole
- lopinavir/ritonavir
- nelfinavir
- nefazodone
- posaconazole
- ritonavir
- saquinavir
- telaprevir
- telithromycin
- voriconazole

1.8. Strong inducers of both CYP3A4 and P-gp:

- avasimibe
- carbamazepine
- fosphenytoin
- phenytoin
- phenobarbital
- primidone
- rifampicin
- St John's wort

